A Randomized Trial to Determine if a Pre-operative Wash With a Chlorhexidine Cloth Reduces Infectious Morbidity in Patients Undergoing Cesarean Section

PI: [name]

NCT02402907

Document Date: July 31, 2019

	Protocol Name:	A randomized trial to determine if a pre-operative wash with a chlorhexidine cloth reduces infectious morbidity in patients undergoing cesarean section
	Principal Investigator/Contact Info:	[name]/[contact] or [name]
	Primary Contact Name/Contact Info:	[name] /[contact] or [name]
	Date Revised:	July 31, 2019
	Study Number:	GCO#14-1410

- **Protocol Title**

A randomized trial to determine if a pre-operative wash with a chlorhexidine cloth reduces infectious morbidity in patients undergoing cesarean section

- **Investigator**

[name]

- **Date Revised *July 31, 2019***

- **Study Number**

GCO#14-1410

Brief Summary of Research (250-400 words):

Surgical site infections (SSI) are the second most common cause of nosocomial infections. In obstetric patients, infectious morbidity (i.e. SSI, endometritis) occurs in 5-10% of cesarean sections, which is 5-fold higher than vaginal deliveries.

Chlorhexidine, chemical antiseptic effective on gram positive and gram negative bacteria, reduces skin microflora/colonization but it is not clear if it decreases the risk of SSI. Chlorhexidine has both bactericidal and bacteriostatic mechanisms causing membrane disruption and is useful against fungi and viruses.

There are no randomized studies evaluating interventions to reduce SSI in patients who undergo cesarean sections.

The study will be offered to women who present for a scheduled primary or repeat cesarean section at Mount Sinai Medical Center. The eligible women will be randomized to use of a 2% chlorhexidine gluconate (CHG) cloth or placebo cloth (a fragrance free cleansing cloth) the night before and the morning of their scheduled procedure. Participants will be blinded to the arm in which they have been assigned. This study intends to show that the use of 2 CHG cloths prior to cesarean section will reduce the rate of SSI.

1) Objectives

The objective of this study is to determine if the use of chlorhexidine gluconate cloths prior to cesarean section reduce the rate of infectious morbidity (i.e. SSI, endometritis).

2) Background

Surgical site infections (SSI) are the second most common cause of nosocomial infections accounting for 15% of all nosocomial infections among hospitalized patients and 38% of nosocomial infections in surgical patients. In obstetric patients, infectious morbidity (i.e. SSI, endometritis) occurs in 5-10% of cesarean sections, which is 5-fold higher than vaginal deliveries. SSI is costly, as evidenced by a two-

	Protocol Name:	A randomized trial to determine if a pre-operative wash with a chlorhexidine cloth reduces infectious morbidity in patients undergoing cesarean section
	Principal Investigator/Contact Info:	[name]/[contact] or [name]
	Primary Contact Name/Contact Info:	[name] /[contact] or [name]
	Date Revised:	July 31, 2019
	Study Number:	GCO#14-1410

fold increased risk of death from SSI. Additionally, there is increased risk of SICU admissions and emergency room readmissions.

Chlorhexidine is a chemical antiseptic that is effective against gram positive and gram negative bacteria and has been shown to reduce skin microflora/colonization. However, it is not clear if it decreases the risk of SSI and other postoperative morbidities. Chlorhexidine has both bactericidal and bacteriostatic mechanisms causing membrane disruption and is also useful against fungi and viruses. Further, chlorhexidine is thought to be more effective than other antiseptic agents because of its rapid action, persistent activity (even when exposed to bodily fluids i.e. blood), and residual lasting effect.

Historically, chlorhexidine has been studied and used in orthopedic and cardiac implant surgeries. Research on the use of chlorhexidine for SSI prevention in cesarean sections is limited. The national average for birth by cesarean section is approximately 32.8% of all births, and the number of deliveries by cesarean section at Mount Sinai Medical Center is comparable. This study intends to evaluate the effectiveness of a preoperative chlorhexidine gluconate (CHG) cloth application and its potential effect in reducing SSI in patients undergoing cesarean section. Patients will be randomized to one of two groups: cloth application with a pre-operative CHG cloth at home on the night before and the morning of surgery (approximately 3 hours prior to the scheduled procedure) or application of a placebo cloth (a fragrance free commercial cleansing cloth).

3) Setting of the Human Research

Research will take place at Mount Sinai Medical Center. Patients will be recruited 2 days before their scheduled cesarean section during their pre-admission appointment on labor and delivery, [REDACTED] of the Klingenstein Pavillion at [name].

4) Resources Available to Conduct the Human Research

Researchers will have access to all patients scheduled for a cesarean section at Mount Sinai Medical Center. About 1800 deliveries by cesarean section occur each year at Mount Sinai. Of these, approximately 1000 are scheduled cesarean sections. Accordingly, there should be approximately 1000 eligible patients per year. Based on our rate of SSI (6%) and the objective of a 67% decrease in SSI rates and expected rate of eligible patients who do not consent at 10%, 683 patients should be in each group for a total of 1365 participants. We aim to recruit 683 patients per group to account for patient drop out or non-compliance.

Eligible study participants will be approached privately on the labor and delivery floor when they come to their pre-admission visit 2 days before their scheduled cesarean section. The nurse who sees patients at this visit will ask if she is interested in participating in the study. If she agrees the

	Protocol Name:	A randomized trial to determine if a pre-operative wash with a chlorhexidine cloth reduces infectious morbidity in patients undergoing cesarean section
	Principal Investigator/Contact Info:	[name]/[contact] or [name]
	Primary Contact Name/Contact Info:	[name] /[contact] or [name]
	Date Revised:	July 31, 2019
	Study Number:	GCO#14-1410

nurse will notify a study team member to consent the patients and is not involved in the cesarean section surgery.

Sage Products Inc, a healthcare product manufacturing company, will be providing the CHG cloths and the placebo cloths, commercial cleansing cloths.

Each research staff member involved in this study has completed all training necessary to conduct human research and the research team has years of experience in clinical research and extensive experience conducting clinical research at Mount Sinai Medical Center.

5) Study Design

a) Recruitment Methods

Eligible study participants will be approached for enrollment during their pre-admission testing visit at the Martha Stewart Center at MSH or the patient's BPP visit at the MFM/OBGYN FPA practice at [name].

Once a patient is consented, she will be randomly assigned to one of the 2 arms of the study: the eligible women will be randomized to use of a 2% chlorhexidine gluconate (CHG) cloth or placebo cloth (a fragrance free cleansing cloth). Participants will be blinded to the arm in which they have been assigned.

b) Inclusion and Exclusion Criteria

The study will be offered to women at > 24 weeks gestation who are scheduled for a primary or repeat cesarean section. Exclusion criteria include allergy to chlorhexidine unplanned or emergency cesarean section.

c) Number of Subjects

We aim to enroll 1356 participants, 678 patients in each group. About 1800 deliveries by cesarean section occur each year at Mount Sinai. Of these, approximately 1000 are scheduled cesarean sections. Based on our rate of SSI (6%) and the objective of a 67% decrease in SSI rates and expected rate of eligible patients who do not consent at 10%, we plan to enroll 1356 patients in total to account for drop-outs or non-compliance. This number was modified last year based on our sponsor monitoring report in order to account for patients who delivered early or forgot to complete the pre-op wipe treatment. We currently have 1,338 enrolled and need 18 more for recruitment completion.

d) Study Timelines

After informed consent has been obtained, the duration of the subject participation will occur from the time they present for preoperative admission

	Protocol Name:	A randomized trial to determine if a pre-operative wash with a chlorhexidine cloth reduces infectious morbidity in patients undergoing cesarean section
	Principal Investigator/Contact Info:	[name]/[contact] or [name]
	Primary Contact Name/Contact Info:	[name] /[contact] or [name]
	Date Revised:	July 31, 2019
	Study Number:	GCO#14-1410

testing until 6 weeks post procedure. We expect to complete enrollment by September 1, 2019 and complete data analysis by November 1, 2019.

e) Endpoints

The primary outcome will be SSI and postpartum endometritis. Secondary outcomes include other maternal complications or interventions, neonatal ICU admissions, maternal length of stay or readmissions.

f) Procedures Involved in the Human Research

This study intends to evaluate the effectiveness of a chlorhexidine gluconate (CHG) shower in reducing SSI in patients undergoing cesarean section. Patients will be randomized to one of two groups: administration of a 2% CHG cloth at home on the night before and approximately 3 hours prior to cesarean delivery on the morning of the surgery or cloth with the placebo (commercial cleansing cloth). Patients will receive a phone call, text message, and/or email reminder to apply the wipes (method of PrepCheck reminder will be decided by the patient). Currently, there is no wash or cloth used prior to cesarean section as a standard of care.

Sage Products Inc will be blinding the study groups. The study team will be provided with pre-prepared packages that contain a 4 digit number indicating the product. Only Sage Products Inc will know which number indicates which group. Patients, recruiters, and statisticians will all be blinded. Once data has been analyzed, Sage Products Inc will inform the study teams as to which packages contain the CHG product number and which contain the placebo.

Each patient will be assigned a unique identification code. The code will be linked to the name and date of birth in an encrypted password-protected linking key code file which will be stored on the PI's personal network folder in the Hospital IT server, accessible by the PI only. The data will be stored in a separate password-protected database by the unique identification code. The database will be stored on a secure desktop at Mount Sinai hospital.

There is minimal risk associated with the use of CHG in a surgical setting. Use of CHG in surgery has been well described in the literature as safe with minimal risks. Enrollment in this study does not place a patient at increased risk over other patients undergoing a cesarean section. The only potential unforeseeable and minimal risk is an allergic reaction to the chlorhexidine gluconate.

	Protocol Name:	A randomized trial to determine if a pre-operative wash with a chlorhexidine cloth reduces infectious morbidity in patients undergoing cesarean section
	Principal Investigator/Contact Info:	[name]/[contact] or [name]
	Primary Contact Name/Contact Info:	[name] /[contact] or [name]
	Date Revised:	July 31, 2019
	Study Number:	GCO#14-1410

Data collected will include demographic variables such as age, parity, BMI, race will be collected, as well as gestational age, number of previous cesarean sections, time from incision to delivery, type of anesthetic, and type of wound closure. Maternal outcomes including EBL, length of incision to delivery, length of operation, type of skin closure, type and use of prophylactic antibiotics, type of skin incision, type of skin closure, indication for cesarean, number of prior cesarean sections, and parity. Charts will be reviewed through the 6 week post partum visit in order to determine how well the skin at the incision site is healing. If patients do not visit Mount Sinai Medical Center for their 2 week wound check, they will be called and asked the following questions: Were you treated for wound infection? Did you experience wound separation or any other wound complications?

g) Specimen Banking

N/A

h) Data Management and Confidentiality

No specimens will be sent out or received in this trial.

All data is de-identified; patients are followed by subject number. Identifiable patient information (consent forms & consent documentation) are kept separately from any data collected. All consent documentation is stored in a locked cabinet at [name]. Identifiable enrollment statistics are kept in a password-protected computer (Excel) spreadsheet that is only accessible by members of the research team on a departmental J Drive.

Data will be analyzed on an intention to treat basis. Statistical analysis will be performed by SAS using X 2 test or Fisher exact test (categorical variables) and student t test or Mann-Whitney U test (continuous variables). Statistical significance will be set at p<0.05.

i) Provisions to Monitor the Data to Ensure the Safety of Subjects

Part I: Elements of a Data and Safety Monitoring Plan

MSSM Principal Monitor:

The principal monitor for this study is the PI:

Last Name: [name]

First Name: [name]

Academic Title: Professor

Department: OB/GYN – Maternal Fetal Medicine

Mailing Address: [REDACTED]

[contact]

	Protocol Name:	A randomized trial to determine if a pre-operative wash with a chlorhexidine cloth reduces infectious morbidity in patients undergoing cesarean section
	Principal Investigator/Contact Info:	[name]/[contact] or [name]
	Primary Contact Name/Contact Info:	[name] /[contact] or [name]
	Date Revised:	July 31, 2019
	Study Number:	GCO#14-1410

[contact]

E-mail: [contact]

[name] has years of experience in research and clinical practice and is qualified to serve as the principal monitor to ensure the safety of participants. All adverse events, subject compliance with the protocol, drop outs, and all study data will be closely monitored and reviewed on an annual basis.

Standard of care and labor floor protocol will be followed in order to ensure standard of care for all cesarean sections.

If there is a temporary or permanent suspension of the study, in addition to the PPHS, the FDA and clinicaltrials.org will be notified.

j) Withdrawal of Subjects

There are no anticipated circumstances under which subjects will be withdrawn from the research without their consent.

6) Risks to Subjects

The risks to subjects are inherent to the cesarean section process itself outside of the study. The only difference in care is use of chlorhexidine gluconate in one arm of the study. This may result in a decreased rate of infection morbidity.

If used as instructed, the only potential unforeseeable risk is an allergic reaction to the chlorhexidine gluconate. Allergic reaction could include itching or hives, swelling in your face or hands, swelling or tingling in your mouth or throat, chest tightness, and/or trouble breathing.

The patients in our study are all scheduled for cesarean section by the patient’s physician. The inherent nature of cesarean section requires an abdominal surgery. As standard of care, all women in this study will be provided with analgesia. In addition, enrollment in this study will not alter the current strategies regarding cesarean section.

There is always the risk of loss of confidentiality; however, there are procedures in place to minimize this risk. To ensure confidentiality, the following system will be adhered to: When subjects are enrolled in this study, they will be assigned a unique identification code. Corresponding medical record numbers for each code (key code) will be stored in a password locked document on the MFM server that can be accessed only by members of the research team. At the conclusion of the data extraction, the outcome variable will be assessed and the key codes to the medical record numbers will no longer be necessary and that information will be permanently erased from the key code file. Electronic data with identifiers will be encrypted according to Data Security Standards.

	Protocol Name:	A randomized trial to determine if a pre-operative wash with a chlorhexidine cloth reduces infectious morbidity in patients undergoing cesarean section
	Principal Investigator/Contact Info:	[name]/[contact] or [name]
	Primary Contact Name/Contact Info:	[name] /[contact] or [name]
	Date Revised:	July 31, 2019
	Study Number:	GCO#14-1410

7) Provisions for Research Related Harm/Injury

The patients will receive standard obstetric care and have access to the obstetric staff (physicians, nursing) as well as all of the resources on the labor floor including the use of the ORs, blood bank, continuous fetal monitoring. Any potential adverse events are inherent to the operative delivery itself and regardless of the study. Any complications that occur during cesarean section will be managed by the obstetricians and anesthesiologists. As standard of care, a physician is present during a cesarean section and is experience in managing complications. The patient is billed as per standard scheduled cesarean section regardless of complications due to the surgery.

8) Potential Benefits to Subjects

Direct benefit to subject is unknown. However, the potential benefit is that we may find a reduction in infectious morbidity related to the cesarean section surgery.

9) Provisions to Protect the Privacy Interests of Subjects

The patients will be approached by the nurse during pre-operative appointment to determine if they are willing to be included for randomization. Their participation will not require any additional examinations. All research-related discussions will be held in a private location. Any questions will be answered and fully discussed to maximize patient comfort. If they choose to participate they will be randomized and receive care within the accepted standards. If a patient must be called to find out how the wound is healing, the research team members placing the class will not leave a message or speak to anyone except the patient herself. When called, she will be asked if she can discuss the research study at that time, ensuring patient privacy and comfort.

10) Economic Impact on Subjects

There are no foreseeable costs that subjects may incur through participation in the research.

11) Payments to Subjects

There will be no payment to subjects.

12) Consent Process

The patient will be consented during the pre-operative appointment and informed consent will be obtained in a private location. As eligible participants had been scheduled for cesarean section prior to arrival, the patient’s doctor has already decided that this procedure is necessary and planned. A copy of the consent form will be available in referring doctor’s offices and the OB clinic, so that subjects will have some information about the study ahead of time, although consent will be

	Protocol Name:	A randomized trial to determine if a pre-operative wash with a chlorhexidine cloth reduces infectious morbidity in patients undergoing cesarean section
	Principal Investigator/Contact Info:	[name]/[contact] or [name]
	Primary Contact Name/Contact Info:	[name] /[contact] or [name]
	Date Revised:	July 31, 2019
	Study Number:	GCO#14-1410

obtained at the time of pre-admission testing. Study participants can be English or Spanish speaking. Resources to translate the consent in Spanish are available. We will be following SOP HRP-090 Informed Consent Process for Research.

13) Process to Document Consent in Writing

Consent will be documented in writing on the form. A copy of the signed informed consent will be placed in the patient’s chart along with a brief progress note indicating study enrollment with a brief discussion of the consent process.

14) Vulnerable Populations

Include	Exclude	Vulnerable Population Type
	X	Adults unable to consent
	X	Individuals who are not yet adults (e.g. infants, children, teenagers)
	X	Wards of the State (e.g. foster children)
X		Pregnant women
	X	Prisoners

15) Multi-Site Human Research (Coordinating Center)

N/A

16) Community-Based Participatory Research

N/A

17) Sharing of Results with Subjects

N/A

18) External IRB Review History

N/A

19) Control of Drugs, Biologics, or Devices

N/A

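### Does the exclusion of unplanned or emergency caesareans in section 5b remove randomised women from the intention-to-treat analysis?

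*Combined protocol and SAP*

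**What the plan says.** All references are to the combined protocol and SAP.

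- **Section 5a (Recruitment Methods)** fixes the time of randomisation: "Once a patient is consented, she will be randomly assigned to one of the 2 arms of the study". Section 3 places recruitment two days before the scheduled operation.
- **Section 5b (Inclusion and Exclusion Criteria)** offers the study to women past 24 weeks who are scheduled for a primary or repeat caesarean, and then states: "Exclusion criteria include allergy to chlorhexidine unplanned or emergency cesarean section". It does not say when the exclusion is judged.
- **Section 5c (Number of Subjects)** says the target was modified "in order to account for patients who delivered early or forgot to complete the pre-op wipe treatment", and that "we plan to enroll 1356 patients in total to account for drop-outs or non-compliance". It adds: "We currently have 1,338 enrolled and need 18 more for recruitment completion".
- **Section 5f (Procedures)** describes coded packages and a placebo cloth: "Patients, recruiters, and statisticians will all be blinded".
- **Section 5h**, in its analysis paragraph, states: "Data will be analyzed on an intention to treat basis". The set is not defined further.
- **Section 5i** says that "subject compliance with the protocol, drop outs, and all study data will be closely monitored".
- **Section 5j (Withdrawal of Subjects)** foresees no removal from the research without the woman's consent.

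**The concern.** Whether a caesarean becomes unplanned or an emergency is often known only after randomisation. An exclusion criterion that names this event without a time point can be read in two ways. On the first, it screens women at enrolment. On the second, it allows a randomised woman to be declared ineligible afterwards and left out.

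The second reading conflicts with intention to treat. It would let the analysis set depend on something that happened after assignment, and the choice between two sets could be made once data are in hand.

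The worry has substance because section 5c reports that early delivery and forgotten wipes were frequent enough to alter the target, yet the protocol does not say how these women are analysed. Few events are expected, so the choice of set could matter to the primary comparison.

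**Working it through.** **1. The passages side by side**

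| Section | Fits enrolment screening, all kept | Fits later removal |
|---|---|---|
| 5b | Placed with the enrolment criteria, directly after the sentence on whom the study is offered to | No time point given; adds little to the requirement of a scheduled caesarean |
| 5c, count | 1,338 + 18 = 1,356, counted in enrolled women | Nothing |
| 5c, reason for the change | Offsets dilution | Replaces lost women |
| 5h | Intention to treat | Nothing |
| 5j | No withdrawal foreseen without consent | Silent on the analysis set |

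Sections 4 and 5c also separate about 1,000 scheduled caesareans from about 1,800 in all when they count the available women. That is the same line as in 5b, drawn at recruitment. No passage says that a randomised woman is removed or replaced.

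**2. The plan's own target**

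Inputs from the protocol are a 6% control rate, a 67% reduction and a significance level of 0.05. The CHG rate is 0.06 × (1 − 0.67) = 0.0198. Two-sided testing is an assumption, and no power is stated. With the pooled-variance formula, 95% power needs 614 per arm, and 614/0.9 = 682.2, rounded up to 683, the figure in section 4. The 95% is inferred from this match. The 678 in section 5c is close to that figure but was not reproduced exactly. At 678 per arm with full use, power is 96.6%.

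**3. What keeping or dropping women would do**

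Let a fraction d of each arm get no benefit and carry the 6% risk. The protocol gives no value for d; 10% and 20% are assumptions.

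- Kept: p₂ = 0.0198(1 − d) + 0.06d, with n = 678 per arm.
- Dropped: p₂ = 0.0198, with n = 678(1 − d) per arm.
- Power = Φ{[(p₁ − p₂)√n − 1.96√(2p̄(1 − p̄))] / √[p₁(1 − p₁) + p₂(1 − p₂)]}, with p₁ = 0.06 and p̄ = (p₁ + p₂)/2.

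For d = 20%, kept: p₂ = 0.0158 + 0.0120 = 0.0278, and power = Φ[(0.837 − 0.568)/0.289] = Φ(0.93) = 82.4%.

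| d | p₂, kept | Reduction, kept | CHG events, kept (678 × p₂) | Power, kept | n per arm, dropped | Power, dropped |
|---|---|---|---|---|---|---|
| 0 | 1.98% | 67% | 13.4 | 96.6% | 678 | 96.6% |
| 10% | 2.38% | 60.3% | 16.1 | 91.5% | 610 | 94.9% |
| 20% | 2.78% | 53.6% | 18.9 | 82.4% | 542 | 92.4% |

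Control events are 678 × 0.06 = 40.7. Power with everyone kept falls to 80% at d of about 22%.

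**4. What the table does and does not measure**

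It models women who never used the cloths. Under intention to treat these women stay in their arm, so their place is not in doubt. The doubtful group is women whose delivery came early or became urgent. Some of them may have used one or both cloths, and some may have delivered vaginally, where section 2 puts infectious morbidity at about one fifth of the caesarean rate. Zero effect and a 6% risk do not describe them, so the table cannot size the effect of the 5b wording.

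**The case for a change.** The best case for a change is this. The inclusion criterion already requires a scheduled caesarean, so at screening the exclusion is nearly redundant. That makes a post-randomisation meaning more plausible, and an analyst could call a converted case ineligible and still label the analysis intention to treat. Section 5j concerns withdrawal from the research, not membership of the analysis set. Blinding limits selective removal by arm, but it does not settle which effect is estimated, and results by coded package could be seen under both sets before the codes are disclosed. A few sentences would close the matter.

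Part of this stands. No passage rules out the second reading in words, and raising the target for early deliveries fits either replacement or dilution. But redundancy between inclusion and exclusion criteria is common and weak evidence of a hidden analysis rule. To adopt the second reading, an analyst would have to act against the one statement in the protocol that governs the analysis set. Even then, removal blind to arm, for an event that nothing in the documents links to the type of cloth, would mainly change the population and the precision; it need not bias the comparison.

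Keeping everyone whatever the mode of delivery would also take more than a line of text. An incision-site outcome needs a scoring rule after a vaginal delivery, and the follow-up in section 5f is built around the wound, so outcomes may not have been collected for every such woman.

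**Conclusion.** The concern does not call for a change. Section 5b is naturally an enrolment criterion, and on that reading it agrees with section 5h: each randomised woman is analysed in her assigned arm, including those who forgot the wipes and those whose delivery came early or became urgent. A stated rule would reach the same analysis and offers no better method.

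The calculation shows no shortfall. With everyone kept, power is 91.5% at 10% and 82.4% at 20% without benefit, and stays at or above 80% up to about 22%. This rests on the protocol's 6% and 67%, an assumed two-sided 5% test, assumed rates of non-use, and zero effect with 6% risk in non-users. It neither shows bias nor measures the effect of the 5b wording.

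What is left is low-severity missing detail: when the exclusion is judged, and how SSI and endometritis are counted after a vaginal delivery. Analysts working under the stated intention-to-treat principle can settle both sensibly while still blinded, and treat any set limited to caesareans that went ahead as scheduled as supportive. The conclusion would differ only if randomised women were in fact being removed under 5b, and nothing in the documents says so.

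### Is the result at risk because the cloth supplier alone holds the package-to-arm code until the analysis is done?

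*Combined protocol and SAP*

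**What the plan says.** One company supplies both products. Section 4 states: "Sage Products Inc, a healthcare product manufacturing company, will be providing the CHG cloths and the placebo cloths". Section 5f gives the same company the blinding. On the form of the code it says: "The study team will be provided with pre-prepared packages that contain a 4 digit number indicating the product". On custody: "Only Sage Products Inc will know which number indicates which group". On who is kept blind: "Patients, recruiters, and statisticians will all be blinded". On release: "Once data has been analyzed, Sage Products Inc will inform the study teams as to which packages contain the CHG product number".

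The study's own key files do not carry treatment. Section 5f says of the participant code: "The code will be linked to the name and date of birth in an encrypted password-protected linking key code file". Section 6 describes a file linking codes to medical record numbers, which is erased after data extraction. The outcome database sits on a secured hospital computer (section 5f).

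Monitoring (5i), withdrawal (5j), risks (6) and research-related harm (7) say nothing about code custody or unblinding of an individual. Section 19, on control of drugs, biologics or devices, is marked not applicable.

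**The concern.** Three features together attract attention. The party that makes both cloths is the only one that knows which is which. It discloses the code after the coded result exists. No independent, dated record is described against which the disclosure could be checked.

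If the two labels were exchanged, nothing in the planned chi-square or Fisher test would show it. The two-sided p-value would be the same and the conclusion would point the other way. A protective cloth would be reported as harmful, or the reverse.

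There is also a safety side. Allergic reaction to chlorhexidine is the one product risk that the protocol names, and no route is written by which a clinician could learn one woman's allocation.

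**Working it through.** **1. What custody of the code can and cannot change.** The p-value depends on the two coded groups, not on their names. Exchanging the rows of a 2 × 2 table leaves the two-sided chi-square or Fisher p-value unchanged and turns the risk ratio into its reciprocal. Sections 4 and 5c plan a 67% reduction, so the risk ratio is 1 − 0.67 = 0.33, and a complete swap would read 1 / 0.33 = 3.03. This holds in every two-arm trial, wherever the code is kept. The documents give no basis for a probability.

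**2. Could the code holder change the mapping to suit the result?** That requires sight of outcomes by package number. The packages are numbered before they reach the study team, so the mapping can reasonably be taken as fixed at that point; only its disclosure comes later. The database is held at the hospital, and no section gives the supplier access to it. The described risk is therefore a clerical slip.

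**3. What a clerical slip would do.** Section 5f does not say whether a number is unique to a package or shared by an arm.

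*Unique numbers.* Let a fraction m of the packages in each of two equal arms be mislabelled, with infection rates p0 (placebo) and p1 (CHG). The observed difference is (1 − 2m)(p0 − p1).

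- Inputs: p0 = 6%, p1 = 6% × 0.33 = 1.98%, true difference 4.02 points.
- m = 1% (about 14 of 1,356): 0.98 × 4.02 = 3.94 points.
- m = 5% (about 68 of 1,356): 0.90 × 4.02 = 3.62 points.
- The sign reverses only if m exceeds 50%, that is, more than 678 of 1,356 packages.

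The values of m are illustrations, not estimates.

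*Shared numbers.* Here one slip would suffice for a swap. It is then also the easiest to check, because testing the contents of a single package of each number settles the matter. The study team handles the packages, and section 5c shows that some were still to be used: "We currently have 1,338 enrolled and need 18 more for recruitment completion". The documents do not say that packages are kept, but they do not support the view that verification is impossible.

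**4. What a second copy would add.** It would be written by the same supplier from the same master list, with 1,338 / 1,356 = 98.7% of women already enrolled. It would catch a change made after it was lodged. It would not catch an error in the master list or in what was packed. It would also create a further place from which the code could leak.

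**5. Reach of the missing release route at 31 July 2019.** Section 3 says: "Patients will be recruited 2 days before their scheduled cesarean section during their pre-admission appointment on labor and delivery". Take a 2-day gap from enrolment to surgery.

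- Still to enrol: 18.
- Enrolled and awaiting surgery, slow case (18 women over the 32 days to 1 September): 18 / 32 × 2 = 1.1.
- Fast case (1,000 scheduled sections a year, 10% refusing): 1,000 × 0.90 / 365 × 2 = 4.9.
- Total: 18 + 1 = 19 to 18 + 5 = 23, or 19 / 1,356 = 1.4% to 23 / 1,356 = 1.7%.

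The slow case ends with the last surgery about 3 September (32 + 2 = 34 days). In the fast case, 18 / 2.47 per day = 7.3 days, so the last surgery falls about 9 days after the document date. Section 5a also allows recruitment at another prenatal visit with no stated gap, so the number awaiting surgery could be higher.

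**The case for a change.** The best opposing argument is that the word Only in section 5f is a positive statement. Read literally, it excludes any other holder, so the gap is more than silence. A sealed, dated list would cost little, could be lodged without unblinding the statisticians, and would make the disclosure checkable. It would have to be lodged before the coded analysis. Section 5c also mentions a sponsor monitoring report, and section 5i an annual review of all study data, so one cannot be sure that nobody outside the site has seen results.

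Some of this stands. The quotations are accurate, no second copy is described, and an independent list is good practice. But section 5c connects the monitoring report with early deliveries and missed applications, not with outcomes by package number, and it does not identify the sponsor. Section 5i makes the principal investigator the monitor, who has no code. An exposure of outcomes to the code holder would have to be assumed.

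On safety, it is true that no release route is written. However, consent and contact pages are not in the available text and could contain one, as could a supply agreement. Section 5b excludes women with known chlorhexidine allergy, and nothing in the plan prevents the site from asking the supplier. A holder of a package list alone could not answer such a request anyway without the woman's package number.

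**Conclusion.** The concern does not hold. If the plan is carried out as written, the comparison is valid: allocation is concealed from everyone at the site, the statisticians stay blind until the analysis is finished, and alpha, power and the p-value do not depend on who keeps the code. Late disclosure is a strength of the design. The remaining possibility, a complete label exchange, is common to all two-arm trials, cannot be given a probability from these documents, and would be only partly guarded against by a second copy from the same source.

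The unwritten release procedure is a missing detail of small prospective reach, about 19 to 23 women (1.4% to 1.7%), falling to none after the last surgery.

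This conclusion assumes that the mapping was fixed when the packages were made and that the supplier had no access to outcomes by package number. The documents point to both but state neither outright. The reach figures further assume a 2-day gap to surgery and the section 5c target of 1,356.
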